3.5 ASSESSMENT OF INTERVENTION

3.5.1 Imaging Protocol and Follow up

Patients will be intravenously injected with:::; 333 MBq (:::; 9 mCi) of radiotracer approximately 60 minutes prior to image acquisition and will be imaged using the GE Discovery PET-CT scanner at UPMC Hillman Cancer Center, UPMC Magee-Women's Hospital, or UPMC Shadyside Hospital. The scanner will be operated in three-dimensional (3D) emission mode on CT attenuation correction as the case may be and images will be reconstructed with manufacturer-supplied ordered subset expectation maximization iterative methods without point-spread function. The field of view for ¹⁸F-DCFPyL PET scans will be vertex to mid-thigh.

The PET images will be evaluated qualitatively by UPMC Hillman Cancer Center (HCC) nuclear medicine physicians. PET scans will be randomly assigned between five PET readers. Interpreters will have at least more than 5 years of PET interpretation and will interpret images. Double reading will be performed for all the PET scans. The readers will be provided with the recent PSA levels and the type of primary therapy (prostatectomy vs radiation therapy) but will be blinded to all other information. The report will indicate the localization of detected lesions either in the prostate bed, locoregional lymph nodes, distant lymph nodes, bones, and/or visceral organs. A scan will be deemed 'positive' if at least one lesion suggestive of disease recurrence is noted. Prostate lesions and lymph nodes will be considered positive if the uptake in those lesions exceeds blood pool activity. Bone lesions will be recorded as positive if the activity is higher than normal bone marrow uptake.

The UPMC HCC nuclear medicine physicians have extensive experience in interpreting FDG-PET/CT scans including those performed with a variety of agents currently used in the research setting. Scans will be interpreted using HE AW 3.2 Volume Viewer software package.

Visual interpretation:

1. Lymph nodes will be deemed positive if the PET scan uptake is focal and greater than blood pool (adjacent or mediastinal blood pool). Pelvic lymph nodes will be subclassified

- according to their localization as follows: R/L obturator, R/L external iliac, R/L internal iliac and other (total of 7 subgroups).
- 2. Visceral lesions will be considered positive if the uptake is focal and greater than physiologic background activity of the involvement organ or the anatomic location.

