 - If patients with solitary visceral metastasis show a decrease of PSA by greater than 50% after targeted treatment (i.e. external beam radiation) and lesions do not change in size (less than 30% decrease or 20% increase in largest diameter).

b. False positive:

- If on follow-up imaging within 3-12 months, sites of initial PET positive lesions seen on CT or MRI scan decrease by more than 30% without systemic therapy or focal therapy at this site.
- If ¹⁸F-DCFPyL PET positive lesions do not meet the criteria for above false positive or true positive findings.
- 3. ¹⁸F-DCFPyL PET positive bone lesions will be considered:
 - a. True positive:
 - If there was a corresponding positive sclerotic lesion on the CT portion of the ¹⁸F-DCFPyL PET in the same location as the focal uptake.
 - If there is focal uptake seen on the baseline bone scan performed within one month of ¹⁸F-DCFPyL PET.
 - If there is a lesion noted on the initial MRI imaging scan performed within one month of ¹⁸F-DCFPyL PET.
 - If within 12 months follow-up CT scan demonstrates development of sclerosis.
 - If within 12 months follow-up MRI scan demonstrates a new bone lesion.
 - If within 12 months follow-up bone scan demonstrates new focal uptake.

b. False positive:

- If ¹⁸F-DCFPyL PET positive bone lesions do not meet the criteria for true positive findings.
- 4. ¹⁸F-DCFPyL PET positive prostate bed and prostate lesions will be considered:
 - a. True positive:
 - If on follow-up imaging within 12 months, lesions seen on CT or MRI scan decrease by 30% (for patients undergoing systemic treatment of focal therapy at this site) or increase by 20% in largest diameter.

• If patients with prostate bed lesions show a decrease of PSA by greater than 50% after targeted treatment (i.e. external beam radiation) and lesions do not change in size (less than 30% decrease or 20% increase in largest diameter).

b. False positive:

- If on follow-up imaging within 3-12 months, sites of initial ¹⁸F-DCFPyL PET positive lesions seen on CT or **MRI** scan decrease by more than 30% without systemic therapy or focal therapy at this site.
- If ¹⁸F-DCFPyL PET positive lesions do not meet the criteria for above false positive or true positive findings.

Histopathology/Biopsy:

- 1. Localization of lesions for histopathology/biopsy will be classified according to the regions in table (Definition of regions) below.

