- 2. The ¹⁸F-DCFPyL PET positive findings will be targeted to be confirmed by histopathology/biopsy if and whenever clinically feasible.
- 3. Histopathological procedures, biopsies and follow-up imaging will be performed as clinically indicated and as per the standard of care/institutional protocol. The following elective procedures may guide the investigator:
 - A. Positive HP/Biopsy: Confirmed sites of metastatic or tumor involvement by histopathology/biopsy will be discussed with the responsible physician/surgeon.
 - B. Negative Biopsy: Patients with suspected tumor recurrence on the PET with negative histopathology/biopsy will be handled as outlined below:

1. Lymph nodes:

- For patients undergoing nodal dissection: Patients will be rescanned with dedicated CT or MRI scan, if clinically feasible, to determine if the suspicious ¹⁸F-DCFPvL PET positive node was removed.
 - o If PET positive lymph node is still present, a repeat biopsy can be pursued if clinically feasible and applicable, or follow-up using imaging as described above will be performed.
 - o If the corresponding node was removed, then this will be considered a False Positive.
- For patients undergoing needle biopsy: Images of the procedure will be reviewed to determine if the correct node was biopsied.
 - o If the correct node was biopsied, then a negative biopsy will be considered a False Positive.
 - o If the incorrect node was biopsied, then follow-up imaging as described above will be performed if clinically feasible.

- 11. Bone lesions: Given the high rate of false negative biopsies for osseous metastases in patients with prostate cancer, patients with negative bone biopsies of PET positive lesions will be further evaluated:
 - If pathology demonstrates alternative diagnoses that is known to be PET positive (e.g. Renal Cell Carcinoma metastases, Paget's disease), then this will be considered a False Positive.
 - If pathology is indeterminate, then follow-up imaging as described above will be performed to determine if the lesion is a True Positive or False Positive.
- Additionally, a repeat ¹⁸F-DCFPyL PET may also be obtained as per treating physician discretion in addition to repeat conventional imaging (CT and/or MRI) in cases of negative biopsy to determine if the biopsy was true negative or false negative.
- C. Although not routinely performed during standard practice, immunohistochemical or specimens (primary and lymph node metastases) may be performed, although not required.

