Table: Definition of regions

Region	Description
1	Prostate bed
2	Pelvis outside of prostate bed (including LNs)
3	Extra-pelvic soft tissue lesions, LNs, visceral metastases
4	Osseous metastases

3.5.2 Screening Assessments

Patients determined to meet the eligibility criteria to participate in the study will undergo Screening assessments as per the Study Schedule of Activities in Appendix A. The following screening procedures will be performed:

- Informed Consent will be obtained prior to any study-related procedures
- Eligibility assessment per the inclusion and exclusion criteria and diagnosis confirmation
- Subject demographics
- Prostate cancer history
- Vital Signs

- Physical examination, including height, weight, body mass index (BMI) and ECOG performance status assessment
- List of concomitant medications (hormonal agents only)
- Lab assessments

3.5.3 **Procedure for Registration of Subjects**

Patients must not start study activities prior to registration. Subjects can be enrolled after eligibility criteria are met. Registration will require the following information:

- Date of consent
- Participant's name
- Date of birth
- Primary study physician
- Confirmation of eligibility

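### Section 3.5.1 has no true-positive rule for positive histology, and checks that the sampled node was the PET-positive one only after a negative result

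*Combined protocol and SAP*

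**What the plan says.** The primary endpoint (Section 2.1.1) is TP/(TP + FP) per patient, with the classification left to Section 3.5.1. The Synopsis and Section 3.10.1 put histology ahead of imaging and PSA in the composite standard.

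The Histopathology/Biopsy part of Section 3.5.1 then says the following.

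- **Location.** "Localization of lesions for histopathology/biopsy will be classified according to the regions in table (Definition of regions) below". The table has four entries: the prostate bed; the rest of the pelvis with all its nodes; "Extra-pelvic soft tissue lesions, LNs, visceral metastases"; and bone metastases.
- **Aim.** "PET positive findings will be targeted to be confirmed by histopathology/biopsy if and whenever clinically feasible".
- **Positive result.** "Positive HP/Biopsy: Confirmed sites of metastatic or tumor involvement by histopathology/biopsy will be discussed with the responsible physician/surgeon". Nothing further is said about classifying a positive specimen.
- **Negative node, needle biopsy.** "Images of the procedure will be reviewed to determine if the correct node was biopsied". The finding is a false positive only if it was the correct node. Otherwise follow-up imaging is used.
- **Negative node, dissection.** A CT or MRI rescan, where feasible, establishes whether the PET-positive node was taken out. If it was, the finding is a false positive. If not, repeat biopsy or follow-up imaging is available.
- **Negative bone biopsy.** An alternative PET-avid diagnosis is a false positive. Indeterminate pathology goes to imaging.
- **Prostate bed and viscera.** No rule for negative histology is given.

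A finer map already exists on the PET side. Under Visual interpretation, "Pelvic lymph nodes will be subclassified" into seven groups, six of them by side. The histology rules do not use it.

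**The concern.** A check made only after one kind of result is not neutral. If the sampled node is negative, someone asks whether it was the right node. If it is positive, nobody is required to ask. Suppose the PET-positive node is benign and cancer is found in another node of the same region. No written rule then stops the PET finding from being called a true positive.

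The protocol's own background makes this plausible at dissection. In J1418 (Section 1.6.1.1) a median of 13 nodes was removed and positive nodes had a median diameter of 3 mm. Packet-level sensitivity was 66.7%, that is 6 of 9 cancer-bearing packets, so PET missed 3 of 9. In OSPREY Cohort A (Section 1.6.1.5) sensitivity was 30.6-41.9%. Both groups were imaged before prostatectomy, so these figures support the mechanism but give no rate for men with recurrence.

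Two things are at stake: whether the primary endpoint can be reproduced from the written plan, and a possible upward error in per-patient PPV. If the site match is not recorded at the time, it may not be recoverable later.

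**Working it through.** **1. The rules side by side (Section 3.5.1)**

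| Specimen | If positive | If negative |
|---|---|---|
| Node, needle biopsy | No site check, no TP rule | Procedure images reviewed; FP only if the correct node was sampled |
| Node, dissection | No site check, no TP rule | Rescan where feasible; FP only if the PET-positive node was removed |
| Bone | No site check, no TP rule | FP if an alternative PET-avid diagnosis; indeterminate goes to imaging |
| Prostate bed, viscera | No site check, no TP rule | No rule |

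The left column is empty throughout. The site-identity check in the right column is confined to lymph nodes.

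**2. The plan's precision, reproduced**

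Section 3.10.2: 300 × 0.85 = 255 PET-positive patients. Exact (Clopper-Pearson) 95% limits:

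| Count | Computed | Stated |
|---|---|---|
| 204/255 (80%) | 74.6-84.7% | 75-85% |
| 214/255 (84%) | 78.8-88.2% | 79-88% |
| 225/255 (88%) | 83.6-91.9% | 84-92% |
| 235/255 (92%) | 88.2-95.1% | 88-95% |
| 245/255 (96%) | 92.9-98.1% | 93-98% |
| 255/255 (100%) | 98.6-100% | 99-100% |

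The table reproduces. The half-width is about 5.1 points at 80%, 4.7 at 84% and 4.1 at 88%. None of this depends on the matching rule.

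**3. Possible size of the unmatched-positive error**

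The documents give none of the three inputs, so all are assumptions:

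- p: PPV if every specimen were matched to the PET lesion; 0.80 or 0.85.
- h: share of PET-positive patients settled by histology; 0.10 to 0.50.
- c: chance that a histology-settled patient with a benign PET lesion has other cancer-positive tissue sampled in the same region; 0.10 to 0.50.

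If every such specimen is accepted as confirmation:

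observed PPV = p + (1 − p) × h × c

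- Smallest, p = 0.85: 0.15 × 0.10 × 0.10 = 0.0015, about 0.2 points (0.0015 × 255 = 0.4 patients).
- Largest, p = 0.85: 0.15 × 0.50 × 0.50 = 0.0375, about 3.8 points.
- Largest, p = 0.80: 0.20 × 0.50 × 0.50 = 0.05, or 5.0 points (0.05 × 255 = about 13 patients).
- Middle, h = 0.33 and c = 0.25: 0.85 becomes 0.862 and 0.80 becomes 0.817, a rise of 1.2 to 1.7 points.

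**4. Why the net direction is open**

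In Section 3.5.1 a PET-positive node meeting neither set of follow-up imaging criteria is a false positive. That default pulls PPV down, including for negatives set aside as the wrong node. For scale only: if 10% (assumed) of truly malignant findings among patients not settled by histology failed the imaging criteria, then with p = 0.85 and h = 0.33 the fall would be 0.85 × 0.67 × 0.10 = 0.057, or 5.7 points. That exceeds the middle upward case above.

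**The case against.** The strongest reply is that the section aims biopsies at the PET-positive findings, and that Section 3.10.1 describes lesion validation by investigators who review images and reports. On that view a positive specimen will normally come from the right lesion. Part of this stands: targeting and review will prevent some mismatches. But targeting applies only where feasible, it does not identify which node in a dissection was positive, and the review has no written criterion for a positive specimen. The plan itself expects that the wrong node may sometimes be sampled.

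Several stronger readings are tempting, and the documents do not support them.

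- **That positive tissue anywhere in a region makes the finding a true positive.** No sentence says so. It can only be inferred from the region table, the region-level definition of false negatives in Section 3.10.1 and the absence of another rule.
- **That errors can only raise PPV.** Wrong-node negatives go to imaging criteria that default to false positive, and a sampling miss in the correct node is also a false positive.
- **That all negative histology must meet an exact-site test.** This is written for lymph nodes only, and the procedures are offered as guidance to the investigator.
- **That per-region PPV is equally biased.** Disease confirmed in the region is the natural truth for that endpoint.
- **That any tumour type counts as confirmation.** The positive-result line concerns communication with the treating physician and is not a definition. The bone rule makes renal cell carcinoma a false positive, and Section 3.10.1 speaks of confirmed prostate cancer.
- **That J1418 measures the effect.** Its PPV is 5/7 = 71.4% by subject and 6/9 = 66.7% by packet. That compares two units of analysis in small numbers and does not isolate specimen matching.

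**Conclusion.** The concern holds in limited form. The top-priority reference standard has no written true-positive rule for positive histology, and the only node-identity check depends on the result. Off-target positives can therefore be counted as true positives, and that component of error is upward.

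Under the assumed ranges it adds about 0.2 to 5 points to per-patient PPV, so it could be negligible or as large as the stated precision. These figures assume that every same-region positive is accepted; informal matching by investigators would make them smaller. Inflation of the reported PPV is a risk and has not been shown. The trial is a single-arm estimation study without a PPV threshold, and the share of patients settled by histology is unknown. Severity: should-fix.

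**What to change.** Add to Section 3.5.1:

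1. Positive histology makes a PET finding a true positive only if it shows prostate cancer and comes from the PET-positive lesion.
2. Positive node specimens get the same correspondence check as negative ones, from procedure images. For dissections where the exact node cannot be identified, the operative label is matched to the side and node subgroup recorded at the PET read.
3. The match is recorded before the pathology result is opened, where possible.
4. Positive specimens that do not match go to the existing imaging and PSA criteria.

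Leave unchanged the exact-node rule for negative nodes, the bone-biopsy rule and the false-positive status of alternative PET-avid diagnoses. Subgroup matching should not replace the exact-node rule for negatives, because it is looser.

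Report per-patient PPV under region-level matching as a sensitivity analysis, so that the effect of the rule is visible.

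The cost is about one paragraph and one case report form field, using procedure images, operative labels and PET subgroups that already exist. A few positive specimens would lose confirming status, so PPV may come out slightly lower.

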3.6 ASSESSMENTS DURING INTERVENTION

3.6.1 Demographic and Medical Record Review

3.6.1.1 Patient Demographics

For this study, demographic information will be reviewed at the Screening Visit and include:

- Date of birth
- Sex
- Self-reported race (American Indian/Alaskan Native, Asian, Black/African American, Native Hawaiian/Pacific Islander, Caucasian, or other)
- Self-reported ethnicity (Hispanic/Latino or Not Hispanic/Latino)

3.6.1.2 Prostate Cancer History

Medical history related to diagnosis to be recorded for each patient consists of:

- Height
- Weight
- Clinically significant diseases
- Surgeries
- Cancer history (including prior cancer therapies and procedures)
- Prior medications (hormonal agents only)

These elements are considered as HIPAA identifiers and will be listed individually in the HIPAA authorization portion of the consent form.

3.6.1.3 Physical Examination

The physical examination will include routine examinations, not including rectal or genitourinary examinations. All clinically significant abnormalities will be recorded in subject's medical record and on the physical exam CRF page. Any abnormality that, in the opinion of the Investigator, is relevant to the safety of the subject or could impact safety or efficacy results for the subject will be considered as "clinically significant". After administration of the first dose of study treatment, each physical exam abnormality that is clinically significant will be recorded as an AE. A complete physical includes an evaluation of the:

- · Head, eyes, ears, nose, and throat
- Dermatological
- Musculoskeletal
- Respiratory
- Gastrointestinal
- Genitourinary
- Neurological systems

Any abnormality identified at baseline should be recorded on the general medical history and baseline conditions eCRF. At subsequent visits (or as clinically indicated), limited, symptom-directed physical examinations should be performed. Changes from baseline abnormalities should be recorded in patient notes. New or worsened clinically significant abnormalities should be recorded as adverse events on the Adverse Event eCRF.

3.6.2 Interventional Examination

During the administration of the study drug, the following assessments will be reviewed:

- Concomitant medications
- Adverse event review (post-injection)

3.7 FOLLOW UP ASSESSMENTS

Following the administration of the study, there will be a post-study follow period and a long term follow up period.

3.7.1 Post-Study Follow Up

For the initial seven days after study drug administration, the following will be reviewed:

- Concomitant medications
- Adverse events

3.7.2 Long Term Follow Up

After the post-study follow up period, the participant will continue to be followed as described in section 3.5.1 Imaging Protocol and Follow Up.

3.8 ASSESSMENT OF SAFETY

3.8.1 Safety evaluation

Patients will be monitored during infusion of ¹⁸F-DCFPyL and for 120 minutes after the infusion. The safety and tolerability of ¹⁸F-DCFPyL Injection will be assessed using the following primary safety outcome measures:

• Incidence, nature, and severity of adverse events up to 7 days following infusion

3.8.2 Radiation exposure from PSMA PET imaging

As part of this scan there is radiation delivered from the ¹⁸F and from the low dose CT or MRI scan that are performed as part of the PET imaging for attenuation correction and co-registration. Although any exposure to ionizing radiation has the potential to cause some harm to tissue, the radiation exposures in this study are comparable to the low-level exposures associated with common diagnostic procedures such as PET/CT scanning. There remains a low theoretical risk of developing a cancer at some point later in life as a result of the radiation exposure received in this study. This risk is much smaller than the clinical risks posed by the patient's current cancer or the salvage radiation therapy the patient might have received or will be receiving. The dose selection process described in section 3.3.5 was aimed at limiting the radiation-absorbed dose to the urinary bladder in accordance with 21 Code of Federal Regulations (CFR) § 361.1 ('.S 50 mGy). Consequently, the 9 mCi administered dose of ¹⁸F-DCFPyL Injection is comparable to the radiation dose of other radiotracers used in oncology such as [¹⁸F]-FDG. The dose range for ¹⁸F-DCFPyL will be 7 - 9 mCi. The approximate Effective Dose for a whole-body attenuation correction CT would be 0.05 rem.

3.8.3 Adverse Events

3.8.3.1 Definition of Adverse Events

Any untoward medical occurrence in a patient or clinical investigation subject administered a pharmaceutical product and which does not necessarily have a causal relationship with this imaging test. An AE can therefore be any unfavorable and unintended sign (including an abnormal laboratory finding), symptom, or disease temporally associated with the use of a medicinal (investigational) product, whether or not considered related to the medicinal (investigational) product.

For this study, AEs are regarded as "intervention emergent," if they occur after study drug has been administered.

Pre-planned or elective surgeries or therapies should be recorded in the patient's source documents but are not to be considered AEs unless there was any change to the patient's medical condition during the AE collection period.

Collection of AEs will occur upon signature of consent.

3.8.3.2 Definition of Serious Adverse Events

An adverse event is considered serious if it results in ANY of the following outcomes:

- Death
- A life-threatening adverse event
- An adverse event that results in inpatient hospitalization or prolongation of existing hospitalization
- A persistent or significant incapacity or substantial disruption of the ability to conduct normal life functions
- A congenital anomaly/birth defect
- Important Medical Events (IME) that may not result in death, be life threatening, or require hospitalization may be considered serious when, based upon medical judgment, they may jeopardize the patient or subject and may require medical or surgical intervention to prevent one of the outcomes listed in this definition

Note: Hospital admission for a planned procedure/disease treatment is not considered an SAE. SAE reporting is required as soon as the participant signs consent.

SAE reporting is required during the 30-day follow up period after the participant's investigational intervention. Any events that occur after the 30-day period and that are at least possibly related to protocol treatment must be reported.

SAE reporting will comply with UPMC HCC SOPs and with local and federal regulations.

